Efficacy and Safety of the Melanocortin Activator Bupropion in Treating Binge Drinking

NCT number NCT03169244 **Document Date** 08/26/2019

Protocol Version 3.1

Efficacy and Safety of the Melanocortin Activator Bupropion in Treating Binge Drinking

Overall Concept: The current proposal represents an innovative pharmacological approach to the treatment of binge drinking that derives from preclinical findings from the laboratory of [name], one of the proposal's consultants. [name] found that a melanocortin agonist, melanoton II, potently suppresses binge drinking (Navarro et al, 2015) in a mouse model of binge drinking. Because the antidepressant bupropion has been shown to activate melanocortin systems in brain (Greenway et al, 2009) [name] lab also studied the effect of bupropion on binge-drinking in their model and showed that bupropion significantly reduced binge-drinking at doses that were lower than those that suppress appetite (unpublished data). Because bupropion is a clinically available and FDA approved medication [name] initiated a discussion with our group to consider a clinical trial of bupropion for binge drinking. Navarro et al (2015) found evidence that using a melanocortin agonist with an opioid antagonist enhanced the potency of the opioid antagonist to suppress binge drinking. In addition to a direct effect on binge drinking may have value in *preventing* progression of alcohol use from binge drinking to dependent level drinking (Thiele, 2012; Navarro et al, 2015)—potentially, a very important finding for clinical care.

The current proposal uses this preclinical and clinical data to design a groundbreaking translational placebo-controlled, Phase IIa clinical trial to 1) assess for an efficacy signal of the melanocortin activator bupropion in binge drinking individuals who have not developed physical dependence on alcohol and 2) to assess for a modulating effect of coexisting nicotine dependence on possible bupropion response. The current proposal is highly novel as it tests the efficacy of activating the melanocortin system in an understudied population (binge drinkers without physical dependence on alcohol.

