Navarro et al (2015) recently demonstrated that activating melanocortin systems with/without opioid receptor antagonism in brain produced a powerful effect to reduce binge drinking in a mouse model. The rationale to test these systems derived from evidence that activation at the melanocortin receptor blunts ethanol intake in animals and that melanocortin peptides and the endogenous opioid β -endorphin share a common protein precursor and functional relationships (See Navarro et al, 2015).

In their study, Navarro et al (2015) used melanotan II (MT-II) to activate the melanocortin receptor and naltrexone for opioid blockade. MT-II reduced bring drinking with MT-II being more potent and overall more effective than naltrexone (72% decrease in ethanol consumption vs 47% decrease), Figure 1. Furthermore, MT-II increased the effectiveness of naltrexone in a synergistic manner. A key aspect of this study was that it investigated effects on binge-drinking rather than dependent level drinking, as the authors note "…our results specifically speak to the possibility that these targets could be useful for curbing excessive binge drinking, an approach that may be useful for preventing the transition to dependence."

Figure 1: Effects of MT-II compared to naltrexone on binge drinking in mice (Navarro et al, 2015).

Advantageously, for human trials, Bupropion (Wellbutrin®), an FDA approved antidepressant and anti-nicotine agent, activates the melanocortin system through proopiomelanocortin neurons likely via norepinephrine and dopamine reuptake inhibition (Greenway et al, 2010; Hasegawa et al, 2005). Thus, we now have access to a pharmacological approach approved in humans to test the hypothesis that activation of melanocortin systems will significantly reduce binge-drinking-- a true translational trial.

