For this proof of concept trial, it is important to use doses of bupropion that are known to be effective and safe for humans. For bupropion we have selected a 300 mg/d dose of the extended release formulation. The 300 mg dose of bupropion is approved by the FDA for depression and for nicotine dependence. The extended release 300 mg formulation has a lower estimated risk of seizures (0.1%) compared to the 0.4% rate for the immediate release formulation. The 0.1% risk of seizures is comparable to the risk reported with other antidepressants such as sertraline and fluoxetine (FDA labels) and with acamprosate (FDA label), which is approved for alcohol dependence. Furthermore, we will be studying a binge drinking population without evidence of physical dependence, a history of seizures, or a reported history of cocaine use so seizure risk is minimized which has been raised as a concern based on animal studies (Silverstone et al, 2008).

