Participants: 50 men and women between the ages of 18 and 44 years of age will be recruited from social media, e-mail list serve to UNC students and staff, and local newspaper/radio advertisements. Key Inclusion criteria: 1) A minimum of 5/3 (men/women) or more binge drinking episodes per month over the past three months (mean population values, CDC (2012)). A binge drinking episode is defined as the consumption of 5/4 (men/women) standard drinks (~12 gms ethanol) in about a two-hour period. Requiring multiple episodes of binge drinking over several months is important to identifying subjects with a consistent pattern of bingedrinking as shorter time frames may give misleading information (see Courtney and Polich, 2009). Subjects may meet DSM-V criteria for mild or moderate alcohol use disorder; 2) BMI ≥18.5 (normal weight or above); 3) express a desire to achieve abstinence or to reduce alcohol consumption. Exclusion criteria: 1) Presence of physical dependence on alcohol as assessed by clear tolerance to alcohol or alcohol withdrawal symptoms based on SCID interview or a Severe Alcohol Use Disorder (>5 SCID DSM-V symptoms); 2) a history of bulimia or a seizure disorder; 3) clinically significant medical disease that might interfere with the evaluation of the study medication or present a safety concern (e.g., renal insufficiency, cirrhosis, unstable hypertension, diabetes mellitus); 4) clinically significant psychiatric illness including any psychotic disorder, bipolar disorder, anorexia/bulimia, severe depression, or suicidal ideation; 5) other substance abuse or dependence disorder other than nicotine or occasional cannabis use; 6) Concurrent use of anticonvulsants, varenicline, MAOIs, any anti-alcohol medication or any psychotropic medication with the exception of stable doses of antidepressants for one month; prior history of adverse reaction to bupropion or naltrexone; 7) AST or ALT > 3.5 times ULN or bilirubin > 1.5 X ULN; 8) positive urine toxicology screen with the exception of cannabis. Individuals with positive cannabis screens will be excluded only if they have a history of a cannabis use disorder; 9) pregnancy or breastfeeding.

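### Exclusion 6 exempts stable antidepressants without carving out bupropion, so a current bupropion user can be enrolled and, in the active arm, would take more than 300 mg/d

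*Combined protocol and SAP*

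**What the plan says.** Criterion 6 in the Participants section lists concomitant drugs that rule a person out: "Concurrent use of anticonvulsants, varenicline, MAOIs, any anti-alcohol medication" and then "any psychotropic medication with the exception of stable doses of antidepressants for one month". The exception is written by drug class. It is not limited by indication, and no individual antidepressant is removed from it. Bupropion appears in the eligibility criteria once, later in the same item: "prior history of adverse reaction to bupropion or naltrexone". Criterion 4 excludes clinically significant psychiatric illness, with "severe depression, or suicidal ideation" among its examples.

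The protocol describes the study drug as an antidepressant. Overall Concept says "Because the antidepressant bupropion has been shown to activate melanocortin systems in brain", and Innovation 1 calls it "an FDA approved antidepressant and anti-nicotine agent".

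The dose paragraph under Research Approach sets the principle that "it is important to use doses of bupropion that are known to be effective and safe for humans", selects 300 mg/d extended release, and gives the seizure rates: "The extended release 300 mg formulation has a lower estimated risk of seizures (0.1%) compared to the 0.4% rate for the immediate release formulation". It adds that risk is kept low by studying people without physical dependence, past seizures or reported cocaine use.

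Trial Design gives active participants 150 mg/d on Days 1-4 and 300 mg/d on Days 5-84, with a three-day step down to 150 mg/d before stopping. Capsules are opaque with matching placebo.

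**The concern.** A rule that admits people on stable antidepressants also admits people on the study drug unless it says otherwise, and this one does not. The authors considered individual agents, since varenicline and MAOIs are named, but current bupropion is not among them.

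The scenario is plausible. The trial aims for about half its participants to be nicotine dependent and accepts treated mood problems short of clinically significant illness. By the protocol's own account, bupropion is approved for both depression and nicotine dependence. Whether bupropion taken for smoking counts as an antidepressant under the exception is unclear, and staff could read it either way.

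What is at stake is participant safety. The dose rationale and the 0.1% seizure figure refer to 300 mg/d extended release. A current user in the active arm would be dosed outside that rationale for most or all of the treatment period.

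**Working it through.** **Does any supplied text close the gap?**

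- Criterion 6: bupropion falls in the exempted class and is not among the drugs named as excluded.
- Criterion 4: removes severe depression and other clinically significant psychiatric illness. This narrows the affected group. It does not empty it, because the antidepressant exception presupposes that some treated people enter.
- Full Eligibility Screening: prescription and over-the-counter drugs are recorded. No bupropion exclusion, washout or dose adjustment is attached.
- Subsequent Treatment Visits: concomitant medication is reviewed, again with no bupropion rule. Study drug may be held or reduced for an adverse event, and is tapered and stopped for sustained high blood pressure. Both act after exposure has begun.

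Nothing in the supplied text excludes current use.

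**Total daily dose, active arm.** The study dose comes from Trial Design. The background dose is not given. I assume it equals one of the protocol's own levels, 150 or 300 mg/d.

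Total = background + study dose.

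| Background (assumed) | Study drug 150 mg/d | Study drug 300 mg/d | Ratio to 300 at full dose |
|---|---|---|---|
| 150 mg/d | 300 | 450 | 1.5 |
| 300 mg/d | 450 | 600 | 2.0 |

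A wider assumption of 450 mg/d background would give 600 and 750 mg/d. Any background dose above zero puts the total over 300 mg/d at full study dose.

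**Days above 300 mg/d.** The text does not make clear whether the three-day taper falls inside Days 1-84 or after them, so both readings are shown. The counts assume the scheduled dose is taken throughout.

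- *Taper on Days 82-84.* Full dose on Days 5-81: 81 − 5 + 1 = 77 days. Study dose 150 mg/d on 4 + 3 = 7 days. A 150 mg/d user is above 300 for 77 days (the other 7 total exactly 300). A 300 mg/d user is above 300 for 77 + 7 = 84 days.
- *Taper on Days 85-87.* Full dose on Days 5-84: 84 − 5 + 1 = 80 days. Study dose 150 mg/d on 7 days. A 150 mg/d user is above 300 for 80 days, and a 300 mg/d user for 80 + 7 = 87 days.

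**Chance of exposure.** For one enrolled user under 1:1 allocation it is 0.50. I give no figure for several users, because that would depend on the stratified blocks.

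**Seizure risk.** The documents give 0.1% for the 300 mg extended-release product and 0.4% for immediate release with no dose stated. Neither applies to a combined dose, so no excess risk can be calculated. Criterion 6 also places no limit on the formulation a person already takes.

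**The case against.** The strongest reply is that no sensible clinician would give study bupropion on top of a known prescription. The exception is naturally read as covering background antidepressants other than the trial drug, and the medication record is taken at the very visit where eligibility is decided. The Protection of Human Subjects section, cited for procedures but not supplied, may contain a rule. Other criteria still apply to the person. The number affected is unknown, the background dose is assumed, and the protocol never calls 300 mg/d a ceiling, so harm is not demonstrated.

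Much of this stands as a limit on the size of the point. A physician may well notice and decline, and the frequency may be zero. Clinicians who see the prescription could work out the largest possible total, although blinding hides whether the participant is actually receiving it.

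It does not remove the gap. The written criterion would tell the physician that the person is not excluded, and safety should not depend on staff overriding it. If a rule exists in the unseen section, criterion 6 contradicts it and should be aligned. The holding and stopping provisions respond to events and do not prevent double exposure. That 300 mg/d is not labelled a maximum leaves intact the point that the protocol's safety argument covers that dose and no higher one.

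**Conclusion.** The concern holds on the supplied text. Applied as written, criterion 6 lets in a current bupropion user who meets the other criteria. In the active arm that person exceeds 300 mg/d from Day 5 at the latest. On an assumed background of 150 to 300 mg/d the total is 450 to 600 mg/d, for 77 or 80 days (150 mg/d user) or 84 or 87 days (300 mg/d user). These figures are per enrolled user and rest on the assumed background dose and full scheduled dosing.

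The claim is that such a person falls outside the protocol's own dose and seizure rationale, not that a particular excess risk has been shown. Dilution of the bupropion-placebo contrast is negligible in an exploratory, unpowered trial and forms no part of it. Confidence is medium, because the Protection of Human Subjects section could not be checked. It should be fixed: the gap concerns the study drug itself and is cheap to close.

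**What to change.** Add a clause to exclusion 6: the antidepressant exception does not extend to bupropion, and current use of any bupropion-containing product, for any indication, is exclusionary. This also settles the ambiguity over bupropion taken for smoking. Apply it through the medication record already taken at screening. For clarity, add a sentence that non-study bupropion may not be started during the 12 weeks; a new start is arguably outside the exception already. Check the Protection of Human Subjects section and align it if it speaks to this.

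With the clause in place, the active-arm dose cannot exceed the planned 150 and 300 mg/d through this route. The cost is a minor amendment with no new data collection, and the loss of any candidates already taking bupropion, a number that is unknown and may be zero.

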**Trial Design**: The design is a 1:1 random assignment to placebo or bupropion XL (300mg/d). [name], the study biostatistician, will prepare the randomization schedule and include blocking by gender. Randomization will be based on a stratified block design, with gender and nicotine dependence as the IRB #16-1064 Master Protocol v.3

stratification variable given some evidence of a moderating effect of nicotine dependence on response to alcohol pharmacotherapy (Fucito et al, 2012).

Bupropion XL will be initiated at 150 mg/d on Days 1-4 and increased to 300 mg/d for Days 5-84. Medication is reduced to 150mg/day for 3 days before being stopped at Week 12 UNC Hospital's Investigational Drug Services (IDS) will prepare opaque capsules containing bupropion XL 150/300 mg and matching placebo. Capsules will be inserted into blister packs with each pack containing 1 week of medication. The IDS will receive the randomization schedule from our statistician [name] and prepare the blister packs according to the blocked schedule with blocking for gender

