Medical Management Intervention: The psychosocial support for the study will be Medical Management (MM) (Pettinati et al, 2005). Drs. [name], [name], [name] and [name] will conduct MM. Drs. [name] and [name] have been trained in MM by [name] and again by [name] of the University of Pennsylvania where [name] was trained as well. [name] has been trained in MM by [name]. MM sessions average 10-15 minutes and focus on three main areas: (1) feedback on consequences of drinking; (2) encouraging compliance with medication/addressing compliance problems and (3) encouraging progress towards drinking goal— reduction or abstinence are acceptable. 10% of sessions will be audiotaped and reviewed to enhance fidelity.

Medication Compliance Monitoring: Participants will record their pill taking in calendar-style diaries that will be provided and collected at each visit. Pills will be distributed in blister packs that will be returned to the study coordinator to reconcile any unused medication from the returned blister packs with participants' diary records.

Statistical Plan and Data Analysis

Outcome Variables: Key outcome variables include frequency of binge drinking, intensity of binge drinking, treatment response, and GGT levels. Frequency is assessed as number of binge episodes/time in trial controlling for missing data (see Statistical Analysis). Intensity of binge drinking is the number of drinks/binge drinking day. Response is defined as no binge drinking in final 6 weeks. Consequences of binge drinking and craving for alcohol will be examined.

Sample Size per Group: In the assessment of feasibility, we need sufficient size to fit our respective models and ensure adequate coverage of our confidence intervals. VanVoorhis and Morgan (2007) provide guidance with respect to minimal sample size needed for differences between groups. They recommend that the groups be no lower than 7 per cell. Our aim is on the effectiveness of bupropion versus placebo in addition to the examination of a potential moderation effect attributable to nicotine use. Assuming a 2:1 ratio between nicotine usage, a sample size of 30 per arm should ensure at least 7-10 per treatment arm as a function of nicotine use. Additionally, our proposed sample size of 30 per treatment arm is in agreement with Sugden et al. (2002) minimum sample size to ensure adequate coverage of nominal 95% confidence intervals, which require n> 28 under minimal skew.

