an analytical procedure which maximizes the statistical power. The Institute of Medicine recommends several approaches, including clustered models, to maximize information from small trials and increase statistical power (Institute of Medicine, 2001). Using the full sample (N=50), we will fit a Mixed Effects Model (MEM) (Schwarz, 1993)) on: %Binge Drinking Days, drinks/binge drinking day, GGT outcomes with the focus on the linear contrasts within the MEM framework examining the superiority of bupropion to placebo. Our modeling will not focus on statistical significance but rather derive confidence intervals for the respective contrasts within the MEM framework examining the superiority of bupropion to placebo MEM accommodates the within-subject correlation of the repeated assessments (weekly for TLFB measures). MEM allows for the inclusion of potential predictors and covariates such as cotinine levels, medication compliance, demographics, and baseline clinical measures such as motivation. Pattern-mixture models (Hedeker & Gibbons, 1997 & 2006) will be used within the MEM structure to assess whether linear contrasts are dependent on attrition/missing data patterns. The pattern-mixture model is dependent on the number of distinct missing data patterns. With this limited sizes study, we will define the patterns as completers vs non-completers as was done by Hedeker & Gibbons (1997,2006). An assessment of significance will not be made but rather we will derive effect sizes of the respective bupropion and placebo contrast for both completers and dropout. With the limited sample and therefore, limited sample per pattern, we realize the respective confidence intervals will be wide. An additional benefit of the MEM is, it will allow us to assess for possible moderators. A moderator is a baseline measure or prerandomization characteristic that has a differential effect on outcome across intervention condition (Kraemer et al., 2002). Moderators are typically defined as variables that significantly interact with condition (Baron & Kenny, 1986; Holmbeck, 1997). The particular moderator of interest is use of nicotine. Assessment of moderation will be made by augmenting our MEM outcome analyses to include the interaction of the effect of assignment (bupropion vs placebo) intervention with the use of nicotine. In a sufficiently sized study, we will have a significant moderator of the assignment effect if the interaction term is significant (Kraemer et al., 2002), where statistically significant interactions would be interpreted by plotting simple regression lines for use versus non-use of nicotine (Holmbeck, 1997; Aiken & West, 1991). With the small sample, we will derive a confidence interval for the respective interaction effect, namely the difference of the differences (the difference between buproprion versus placebo for nicotine users versus the difference between buproprion versus placebo for the nicotine abstainers). Subsequently, we will perform a corroborative set of analyses, in accordance with Kianfiard & Islam (2011), where summary measures over the entire TLFB period are derived. Simple ANOVA/ANCOVA models will be used to perform the above analyses with the model structure producing confidence intervals for both the buproprion versus placebo contrast, as well as the moderation assessment.

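### The sample-size section argues for 30 per arm and claims to satisfy n>28, but the trial recruits and analyses 50 at 1:1, which is 25 per arm

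*Combined protocol and SAP*

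**What the plan says.** Under Statistical Plan and Data Analysis, the paragraph Sample Size per Group gives the purpose of the sample size: "we need sufficient size to fit our respective models and ensure adequate coverage of our confidence intervals". It then offers two supports, both tied to 30 per arm.

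- **Cell size.** Of the first cited source it says "They recommend that the groups be no lower than 7 per cell". With an assumed 2:1 nicotine split, it concludes that "a sample size of 30 per arm should ensure at least 7-10 per treatment arm as a function of nicotine use".
- **Interval coverage.** It says that "our proposed sample size of 30 per treatment arm is in agreement with" a second cited source's "minimum sample size to ensure adequate coverage of nominal 95% confidence intervals, which require n> 28 under minimal skew".

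Three other places fix the size of the trial:

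- Participants: "50 men and women between the ages of 18 and 44 years of age will be recruited".
- Trial Design: "The design is a 1:1 random assignment to placebo or bupropion XL (300mg/d".
- Statistical Analysis: "Using the full sample (N=50), we will fit a Mixed Effects Model (MEM".

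Statistical Analysis also says that the analyses are exploratory and unpowered, and that confidence intervals rather than significance tests will be the output. The section on nicotine as a potential moderator sets a recruitment target of about half with nicotine dependence.

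**The concern.** Thirty per arm at 1:1 is 60 participants, whereas the protocol recruits and analyses 50. The two figures describe different trials, and nothing in the document links them. The support offered for interval coverage holds for 30 per arm and does not hold for the size that follows from 50 at 1:1.

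This matters because the plan has no power calculation to fall back on. It names interval coverage as a reason for its size, and it reports intervals for every outcome. A reader of the sample-size paragraph would therefore credit the trial with a size and a design property that it does not have, and could not tell whether 50 or 60 was intended. Only the stated justification and the precision are affected. No power claim, model or decision rule depends on it.

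**Working it through.** **Inputs, all from the protocol**

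- Arm size used in the justification: 30 (Sample Size per Group, stated twice).
- Coverage criterion: n>28, so at least 29, applied there to the arm size.
- Cell criterion: no fewer than 7, with an assumed 2:1 nicotine split (same section).
- Number recruited: 50 (Participants). Allocation: 1:1 (Trial Design). Number analysed: 50 (Statistical Analysis).
- Nicotine recruitment target: about 50% (section on nicotine as a moderator).

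**1. The plan's own figures.** At 30 per arm the paragraph is consistent: 30 > 28, and a 2:1 split gives a smaller cell of 30/3 = 10, the top of its stated range of 7 to 10. The implied total is 2 × 30 = 60.

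**2. The trial as described.** 50/2 = 25 per arm. The protocol does not print this figure, but it follows directly from the total and the allocation. 25 is not greater than 28.

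**3. Shortfall.** The smallest 1:1 total with both arms above 28 is 2 × 29 = 58, and 58 − 50 = 8.

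**4. Other readings.**

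- *Dropout.* Going from 60 to 50 would need a loss of 10/60 = 1/6. No dropout rate is stated, and 50 is the number recruited as well as the number analysed.
- *Unequal arms.* Allocation is 1:1, and no split of 50 puts both arms above 28.
- *n>28 as a total.* The sentence compares it with the size of each treatment arm.

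None of these reconciles the figures.

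**5. The 7-per-cell rule.** Expected smaller nicotine cell per arm:

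| | 25 per arm | 30 per arm |
|---|---|---|
| 2:1 split | 25/3 = 8.3 | 30/3 = 10 |
| 50% target | 25/2 = 12.5 | 30/2 = 15 |
| Smallest share giving 7 in expectation | 7/25 = 28.0% | 7/30 = 23.3% |

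The plan's 2:1 assumption (33.3%) clears both limits, so this rule survives in expectation, with less margin. If nicotine status varied binomially with probability 1/3 (my assumption, not the plan's), the chance of at least 7 in the smaller cell of one arm would be 0.78 at 25 per arm and 0.92 at 30.

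**6. Precision.** This step covers only the corroborative ANOVA with one summary value per participant, before dropout and covariates. The 95% half-width for the arm contrast, in SD units, is t(0.975, 2n−2) × √(2/n):

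- n = 25: 0.569
- n = 30: 0.517
- ratio: 0.569/0.517 = 1.10, so about 10% wider

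These figures do not describe the mixed, logistic, Cox or ordinal models.

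**The case against.** The strongest reply is that little depends on this. The plan calls itself exploratory and unpowered, refers to its small sample, and warns that intervals will be wide when it discusses the missing-data patterns. The 7-per-cell statement survives: the 8.3 expected at 25 per arm lies inside the plan's own range of 7 to 10, so only the number 30 is wrong there. The n>28 figure comes from a source that cannot be checked here, so whether it was meant for a single mean, an arm mean or a two-arm contrast is unknown. It is also conditional on minimal skew, and Statistical Analysis provides for checking skew and transforming where needed. An arm of 25 may therefore give perfectly acceptable coverage.

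Most of this stands, and it limits the weight of the point. The fault lies between sections, since the sample-size paragraph is sound on its own terms. Missing the threshold does not show that the intervals undercover, and the half-widths above illustrate precision in a secondary analysis only. But general warnings about a small sample neither withdraw the specific claim of agreement with n>28 nor say whether 50 or 60 is the sample size.

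**Conclusion.** The point holds. The sample-size paragraph justifies 30 per arm, while the trial as described has 25. At 25 the claimed agreement with n>28 is false on the plan's own use of that criterion, by 4 per arm (29 − 25) or 8 in total. The conclusion needs only the stated total, the stated allocation and the criterion as the plan quotes it. It does not depend on whether the criterion is a good one.

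The consequence is modest: the stated basis for interval coverage is lost, and intervals in the simple summary-measure analysis are about 10% wider than at 30 per arm. The correction should be made because the contradiction is certain, it concerns the trial's main form of output, and it is cheap to repair.

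**What to change.** State one sample size in Participants, Sample Size per Group and Statistical Analysis. With 50 retained, rewrite the sample-size paragraph for 25 per arm and remove the statement that the design agrees with n>28. Suggested text:

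> Fifty participants will be randomised 1:1, giving 25 per arm. Under an assumed 2:1 nicotine split, about 8 per arm are expected in the smaller nicotine group (12 to 13 if the 50% recruitment target is met). The expected cell size is at least 7 provided that group makes up at least 28% of participants. An arm of 25 is below the n>28 cited for 95% interval coverage under minimal skew.

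The 28% condition concerns expected numbers: 28% of 50 is 14 people, which gives 7 per arm only if they divide evenly. Stratifying on nicotine dependence makes that likely but does not guarantee it.

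Optionally, add an expected 95% half-width of about 0.57 SD for the arm contrast, labelled as applying to the summary-measure ANOVA before dropout and covariates.

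The cost is wording only, with no extra participants. The stated justification becomes slightly weaker, because the n>28 support goes and the expected smaller cell is about 8 rather than 10.

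If 30 per arm was in fact intended, Participants and Statistical Analysis should read 60 and the sample-size paragraph can stay. That costs 10 more participants than the protocol now states.
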